5.2. Eligibility

Eligibility criteria are based on self-reported information from study participants.

Inclusion Criteria:

- Individuals must be between 18 and 55 years old.
- All participants will not be tobacco smokers and will be well-nourished according to standard anthropometric criteria with BMI between 18.5 and 32.
- Individuals must be able to give informed consent.
- Subjects willing and able to:
 - consume prebiotics or placebo preparations for a period of 4 weeks
 - record daily food consumption using hard-copy food diary provide at the baseline visit, and complete the Diet History Questionnaire (DHQ).
 - provide stool, and blood (via venipuncture) samples.
- Enrollment will not be restricted based on race, ethnicity, or gender. Subject population will reflect the population providing a broad selection of individuals to allow to enroll subjects from all races, ethnicities and genders as represented in North Carolina state.

Exclusion Criteria:

- Individuals diagnosed with Inflammatory Bowel Diseases (IBD), Ulcerative Colitis (UC), Colorectal Cancer (CRC) , or diabetes mellitus.
- Celiac disease or IBS diagnosed by a physician

- Lactose intolerance as diagnosed by a hydrogen breath test
- C. difficile infection or treatment within 2 months
- Individuals currently or within the past 2 months on prescribed antibiotics.
- Patients with a history of gastric bypass surgery.
- Any physical or psychological condition that, in the opinion of the investigators, would pose unacceptable risk to the patient or raise concern that the patient would not comply with protocol procedures
- Women that are pregnant or breastfeeding will be excluded from the study.
- A response of 4 or 5 to questions 2 (abdominal pain), 6 (abdominal discomfort), 8 (constipation), 16 (diarrhea), 22 (abdominal distention), 26 (abdominal bloating), 31 (nausea), or 33 (vomiting) on the PROMIS Gastrointestinal Symptom Scale.

5.3. Strategies for Recruitment and Retention

Recruitment Strategy:

Subjects will be recruited using study flyers and/or asked to participate in the study via email or phone call. Only if the subject agrees to participate and meets enrollment criteria will they be enrolled in the study. Subjects will be screened by the Clinical Research Coordinator on the basis of inclusion and exclusion criteria laid out in this study. Only individuals with no formal diagnosis of IBD, IBS, UC, CRC, celiac disease, or diabetes mellitus will be selected as study participants based on a self-report. Also, individuals with a history of gastric bypass, current use of antibiotics or use of oral antimicrobials in the past 2 months will be excluded. The PI will review subject enrollment at weekly project meetings so that any deviation from the anticipated enrollment schedule will be detected quickly. All outreach and advertising activities will also be reviewed on a weekly basis.

Retention Strategy:

The PI and research team will hold weekly project meetings to monitor enrollment and ensure enrolled subjects complete all study procedures as intended. Likewise, brief weekly contacts (either by phone, email, or text message) with enrolled subjects will follow up regarding protocol adherence, gastrointestinal symptoms, and study satisfaction, in addition to any protocol-specific procedures. This approach provides the opportunity for early identification of possible reasons for study non-adherence or early discontinuation by the subject and to address such issues, if possible. If a subject decides to withdraw participation in the study, the date and reason will be recorded and stored in the RedCap database. On a weekly basis, the study coordinator will run a report on participants accrual and completion status for review by team to identify and resolve any problems or potential issues that arise during the course of the study.

Screen Failures:

During the screening period, inclusion/exclusion criteria for the study participation will be checked / tested. Subjects who meet all inclusion criteria and do not meet any exclusion criterion will be eligible to be randomized. Those who are not eligible for randomization or dosing will be considered as screening failures. In the case of screen failures, the reason will be recorded. We expect a 20% screen failure rate.

5.4. Consent Process

Potential participants will be approached via email or text message, and a virtual screening appointment will be set up over Zoom. The study will be explained to the subjects by [name] or Clinical

Research Coordinator, [name]. Potential participants who meet screening criteria and are still interested in the study will undergo consent procedures. Consent will be performed virtually using the Qualtrics platform. Potential participants will be allowed time to read the consent and all questions will be answered. Consent discussion will take place until the subjects are fully aware of all study details and all questions have been answered. There is no set time for consent discussion. Subjects will be told that they can withdraw from the study at any time without penalty. The subject and investigator and/or study coordinator will sign the consent form. An electronic version of the consent will be provided to the participants and printed copy will be provided to the subject at the time of the first study visit.

6. Study Intervention

6.1. Intervention – Test Article (if applicable)

Description: Prebiotic galacto-oligosaccharides (GOS) have an extensive history of safety and have been used for decades to improve overall host health via modulation of the gut microbiota⁴⁰. Since GOS are complex carbohydrates resistant to digestion in the upper gastrointestinal tract that arrive to the colon intact, they increase the abundance of specific primary and secondary degraders expanding the probiome, autochthonous beneficial members of the intestinal microbiota⁴¹. Specific increases of *Bifidobacterium* (the “bifidogenic effect”) hence are fundamental to the beneficial effect of the prebiotic that result in increased concentration of colonic short chain fatty acids (SCFAs), particularly butyrate⁴². Over 95% of the microbially generated SCFAs are absorbed by the colonic epithelium⁴³⁻⁴⁵. The three major SCFAs (acetate, propionate and butyrate) stimulate proliferation of normal crypt cells and intestinal barrier integrity. Butyrate and, to a lesser degree, propionate, have been reported to inhibit growth of colon cancer cell lines⁴⁶. Furthermore, butyrate has potent immunomodulatory effects influencing activity of HDACs responsible for decreasing dendritic cells IL-12 and IL-6 cytokine secretions⁴⁷, and induces T_{REG} cells and IL-10-secreting T cells through Gpr109a on colonic dendritic cells and macrophages⁴⁸.

The prebiotic GOS and hGOS in this formulation are generated by the β -hexosyltransferase from *Sporobolomyces singularis*, optimized and heterologously expressed to generate high-purity GOS^{49, 50}. Commercial GOS are a mixture of mono, di, and oligosaccharides in varying ratios. Although major advances that have led to standardization, and better characterization and reporting of such mixtures have been made, variability in the GOS composition impacts the reproducibility of studies and interventions as well as the ability to predict outcome. GOS are currently produced commercially by trans-galactosylation of lactose as donor and acceptor substrate by β -galactosidase enzymes (EC 3.2.1.23)⁵¹. Converting lactose into GOS by β -galactosidases is a kinetically controlled reaction, by the competition between hydrolysis and trans-galactosylation. During this conversion, the thermodynamically favored hydrolysis of lactose, which generates D-galactose and D-glucose, competes with the transferase activity that generates a complex mixture of various galactose-based di- and oligosaccharides of different structures⁵². Vivinal GOS is produced by *Bacillus circulans* β -galactosidase, Bimuno is a GOS blend derived from lactose conversion using *Bifidobacterium bifidum* NCIMB 41171 enzymes, and Oligomate is produced by the β -hexosyltransferase from the yeast *Sporobolomyces singularis*.

GOS may have a degree of polymerization (DP) up to 9. However, the enzymatic generation of GOS tends to produce low molecular weight oligosaccharides. As shown in Table 1, concentration of

disaccharides in commercial formulations can be as high as 52%. DP2 elements may differ in their structure. One seminal study⁵³ that reported the generation of GOS by *B. circulans* showed that the β -(1-3), β -(1-2), and β -(1-6) linked galactosyl disaccharides (D1-D3) were formed by the trans-glycosylation reaction with the β -galactosidase from *B. circulans*. Since lactose [the β -(1-4) linked galactosyl-disaccharide] was already present in the initial reaction as substrate, the authors used a different reaction (containing *p*NP-Gal and glucose) to confirm lactose synthesis by the enzyme.

In a recent study⁵⁴, the analysis of 6 commercial GOS products using high-performance liquid chromatography (HPLC) size exclusion on a Rezex RSO-oligosaccharide Ag⁺ column showed that all tested prebiotics had the monosaccharides galactose (Gal) and glucose (Glc) together with DP2 (mostly lactose) up to DP5 oligosaccharides in detectable levels. Vivinal GOS, and two other GOS products had also detectable amounts of DP6 oligosaccharides. Interestingly, except for one GOS product, the DP2-DP4 fractions of the various products comprised >90% of all GOS components, with most products containing a majority of DP2, with exception of one GOS product that had the highest DP4, DP5, and DP6 content of all GOS products with very low amounts of Gal and Glc, indicating a DP-based purification step. This study is one of the most detailed studies on composition of GOS; however, it does not provide the names or sources of 6 of the 7 analyzed compounds. Another study that reported on impact of B-GOS (Bimuno, Clasado Limited) on the immune system of 40 elderly individuals stated that 52% of the product was DP2²⁹. In contrast, RP-G28, a purified preparation reported <3.2% of DP2 oligosaccharides¹¹ (Table 1).

Table 1. Composition of prebiotic GOS commercial formulations

	RP-G28 ¹¹	Vivinal ⁵⁴	Bimuno* ²⁹	BIOLIGO® GL 700 **	Oligomate
Degree of polymerization					
DP2	<3.2%	42.55 \pm 0.22%	52%	17.5%	14.8%
DP3	56-59%	23.63 \pm 0.20%	26%	38-52%	34.4%
DP4	26-30%	10.21 \pm 0.23%	14%		
DP5		3.00 \pm 0.17%	8%		
DP6	11-16%	0.39 \pm 0.17%			
Glucose	<0.1%	18.52 \pm 0.12%		22%	22.4%
Galactose	<0.1%	1.70 \pm 0.08%		0.8%	8.6%

*Bimuno = B-GOS (Clasado) = Clasado BioSciences Ltd. (St. Helier, Jersey, UK) = HOST-G904 (Therabiomics, Jersey, Channel Islands)

** BIOLIGO® GL 5700 GOS (Ingredion) = Purimune (GTC Nutrition, Golden, Colorado [2008])

To ensure the safety of the human volunteers we followed the FDA guidance for deriving the maximum recommended starting dose (MRSD) for clinical trials of new molecular entities in adult healthy volunteers. See: U.S. Department of Health and Human Services Food and Drug Administration. (2005). *Guidance for Industry: Estimating the Maximum Safe Starting Dose in Initial Clinical Trials for Therapeutics in Adult Healthy Volunteers*. Rockville, MD: Center for Drug Evaluation and Research (CDER), 7.

The equation used is as follows:

$$HED (mg * kg^{-1}) = Animal Dose (mg * kg^{-1}) * Animal K_m / Human K_m$$

Where the K_m factor is a number based on body surface area. In our animal study we used a dose of 1,500 mg kg⁻¹, based on ~30 mg LacNAc fed to a ~20 g mouse per day²⁵. We used a K_m factor of 3 for mice and 37 to represent a 60 kg human adult.

We can consistently produce hGOS containing concentrations that exceed 25 g/L of LacNAc with no significant variation between batches observed. Therefore, our approach is to normalize to reach the proposed dose levels using pure GOS. The active component is in power form that will be obtained after lyophilization. Concentration will be confirmed using previously developed HPLC protocols³³

Acquisition: [name], Professor of Plant and Microbial Biology at North Carolina State University and Co-investigator in this proposal, will coordinate with the Golden LEAF Biomanufacturing Training and Education Center (BTEC) the cGLP production of the prebiotics galacto-oligosaccharides (GOS) and GOS enriched in N-acetyl-D-lactosamine (LacNac, humanized GOS, hGOS) for the clinical intervention planned for the study. BTEC has the capabilities, equipment, and expertise for the bioprocess cGLP production (See Appendix 1).

Formulation/Packaging/Labeling: GOS, hGOS, and placebo will be supplied as a sterile powder by BTEC, dried and portioned into daily dose pouches under sterile conditions at the NC Food Innovation Lab, Kannapolis, NC, . Pouches will be labeled and will serve to protect the preparations from light, air,

Protocol Number:
Study Acronym: GOS Pilot

Enrollment ID:

Lot No.:

Subject Number:

Subject's Initials:

Date Dispensed:

Contents: 56 pouches, 5 g each for the first 10 days followed by 7.5 grams each for days 11-28 of GOS, hGOS or matching placebo, plus two additional packets (one 5mg and one 7.5mg) for inadvertent loss or spillage.

Directions: Use only as directed. To be taken by mouth with food or beverage.

This product is an investigational product to be dispensed only by a qualified investigator.

Storage: Room Temperature 15-30 °C (59-86°F)

Caution: New drug limited by law to investigational (clinical trial) use only. Keep out of reach of Children.

Manufactured By: Golden LEAF Biomanufacturing Training and Education Center (BTEC), [name]

Distributed by:

and moisture. Product will then be transferred to the UNC Investigational Drug Services (IDS).

Storage and Stability:

The powder prebiotics galacto-oligosaccharides (GOS), GOS enriched in N-acetyl-D-lactosamine (LacNac, humanized GOS, hGOS), and placebo can be safely stored in a dry area at room temperature and hold an expiration date of 2 years after production.

Preparation and Administration: Individuals will be provided with a total of 58 pouches numbered by day (#1 to #56) containing the appropriate daily dose of treatment or placebo. Pouches 57 and 58 will be extra pouches in case of loss or spillage. Participants will be instructed to consume one pouch twice a day. The premeasured powder can be added to hot or cold non-alcoholic beverages or sprinkled over food.

Modification: Individuals experiencing more than three of the following side effects a day: bloating, flatulence, belching, abdominal pain, discomfort, watery stool, and vomiting will be instructed on how to spread out the daily dose to minimize side effects. Participants experiencing these side effects be asked about frequency and severity. Severe side effects interfering significantly with subject's usual function will result in withdrawal from study. Weekly phone contacts will allow for timely report of adverse effects. Participants will also be given the choice to contact the study PI directly in case of emergencies.

Accountability: UNC Investigational Drug Services (IDS) will keep source documentation for accountability of the study treatments that will detail receipt, dispensing, and return of used and unused prebiotics and placebo. Treatment products will be stored in locked facilities until they are either returned to the PI at the end of the study. Prior to dispensing, sachets containing the treatment will be visually inspected. If the package appears to have tears or sign of tampering, the sachet will be rejected for use but retained until the end of the study. At the end of the study, the study team will determine dispensation of all remaining unused treatment packs at the study site. An accountability log will be kept, indicating the final disposition of study treatment. This log will be provided to the PI at the end of the study.

6.2 Assignment Procedures

Matching and Stratification:

N/A

Randomization, Concealment, and Blinding:

The Excel RAND function will be used for simple randomization of participants into the 3 different groups. The PI and designated study personnel are blinded to the randomization and are responsible for following the randomization and blinding procedures described in each clinical trial protocol.

Masking (Blinding):

This is a double-blinded study. The master randomization codes will be kept by IDS with appropriate security measures and access control. The research team will be unblinded once all of the samples have been collected and processed, before data analysis.

Unblinding. Circumstances for unblinding will be clearly established before the first patient begins treatment. Randomization procedures, if any, will be followed to ensure the code is broken only in accordance with the protocol. The study codes will be stored at the study site or may only be available directly from IDS. The code will only be broken in the case of an adverse event where it is necessary for the PI to know which treatment the individual is receiving before the individual can be treated. If it is

necessary to break the blind, the researcher will notify the IRB and document the event, together with the reasons for breaking the code.

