Target Population	
Healthy adult individuals
 
Key Inclusion Criteria: Individuals ages 18-55 with BMI of 18.5 to 32.
 
Key Exclusion Criteria:
 
 Formal diagnosis of IBD (including ulcerative colitis, Crohn's Disease) colorectal cancer, diabetes Celiac disease or IBS diagnosed by a physician Lactose intolerance as diagnosed by a hydrogen breath test C. difficile infection within 2 months Antibiotic consumption in the previous 2 months History of gastric bypass surgery Current tobacco smoker Pregnant or breastfeeding A response of 4 or 5 to questions 2 (abdominal pain), 6 (abdominal discomfort), 8 (constipation), 16 (diarrhea), 22 (abdominal distention), 26 (abdominal bloating), 31 (nausea), or 33 (vomiting).
Numbers of Participants	
Number to be recruited for screening: 55-60 participants
 
Number of eligible participants enrolled: 48 adult individuals

Clinical Phase	Pilot
Intervention	Daily oral administration of 10 - 15 g of Prebiotic galacto-oligosaccharides (GOS) or GOS enriched with lactosamine (LacNAc) for four weeks
Study Description	We will enroll 48 adult individuals (18-55 y.o.). Subjects will be assigned randomly to one of 3 groups (n = 16): GOS, hGOS or placebo (powdered corn syrup comprised of fructose, glucose, and an inert cellulose material that matched the consistency, color, sweetness, and taste of the prebiotics) to test safety and dose tolerability. The prebiotic treatment will last for 4 wk. Before the treatment (baseline) and during week 4 of the trial (after the prebiotic treatments), we will assess changes in quality and quantity in bacterial components of the gut microbiome pre- and post-treatment. Likewise, we will

	determine serum markers of inflammation, integrity of the intestinal barrier at baseline and at week 4. Participants will complete the Diet History Questionnaire (DHQ), a freely available food frequency questionnaire (FFQ) at baseline and will be asked to maintain a record of their daily diet by using a printed meal tracking diary. In addition, the PROMIS Gastrointestinal Symptom Scale will be used for potential side effect evaluation at baseline and each week for the duration of the study.
Outcome Measures	Dose safety and tolerability in healthy adults . Gut microbiome Inflammation Integrity of intestinal barrier
Study Duration	4 weeks
Subject Participation Duration	4-5 weeks
Estimated Time to Complete Enrollment	40 weeks

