Obtain informed consent. Screen potential participants by inclusion and exclusion criteria; obtain medical history, document. **Total N = 48**

Visit 1

Time Point

Weekly GSSC data collection

Visit 2
Time Point

4 weeks: collect blood and stool. Administer 38-point Gastrointestinal Symptom and Severity Checklist (GSSC) Questionnaire (FFQ)

Analyses: (a) Evaluation of inflammation and intestinal barrier function in serum; (b)

4.1.Treatment Design

Dose rationale. The intervention will include a dose ranging between 10 to 15 g daily as previously reported¹⁰. Doses were selected based on previous literature reports^{16, 17, 28-30} and the interventions conducted by our group to assess efficacy of GOS in lactose-intolerant individuals^{10, 11, 31, 32}. The hGOS preparation will be composed of GOS enriched with LacNac at a concentration of 6.7-31 μ g/mL (<1% of the formulation), which is in the range found in human breast milk³³ and hence considered safe.

Regimen. The prebiotics dose will be 5 grams twice daily on days 1–10 followed by 7.5 grams twice daily on days 11–28. The placebo (powdered corn syrup comprised of fructose, glucose, and an inert cellulose material that matched the consistency, color, sweetness, and taste of the prebiotics) will be administered in a blinded matching packet at the same doses. If participants miss taking a dose on a given day, they will be directed to put the pouch for that day aside, and on the next day take the next numbered pouch.

4.2.Experimental / Observational Design

Subjects will be assigned randomly to one of 3 groups (n = 16): GOS, hGOS or placebo.

4.3.Measurement Design

Blood and stool samples will be collected at baseline (Day 0) and end of treatment (Day 28). Stool collection kits will be provided to participants in case samples cannot be obtained *during study visits*. Safety and tolerability will be determined based on the severity and/or frequency of side effect using a 38-point Gastrointestinal Symptom and Severity Checklist (GSSC). In addition, tolerability will be evaluated through occurrence of drop-out and adherence.

Measurements on blood (10 mL per visit for a total of 20 mL):

- (1) Fasting venous blood samples will be drawn and serum will be used to quantify zonulin using the Zonulin (IDK® Zonulin) (Serum) ELISA test (Immundiagnostik AG).

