8.6. Variables Representing Treatment

A total of 45 individuals will be randomized 1:1:1 (placebo, GOS, hGOS) to treatment. Allowing for a 20% drop out rate, approximately 55 - 60 subjects will be enrolled.

9. Statistical Analysis Plans

a. Strategies that Apply to all the Specific Aims

- (1) To help ensure replicability of the research, the analysis plans will be reviewed and finalized prior to collection of data (a priori). For the specific aim, the analysis plan specifies detailed steps for obtaining estimates of population parameters (e.g intervention safety) and for making inferences.
- (2) Sensitivity analyses will be performed to assess the robustness of the major results as indicated by their sensitivity to reasonable perturbations of the choices of the methods and assumptions used. Any question about the optimal choice of methods and assumptions are best handled by relegating competing approaches to roles in the domain of sensitivity analyses. Results of the sensitivity analyses will be used to guide our level of trust in the main results. Best practices for dealing with incomplete data will depend on the documented causes of missing, censored, and coarsened values. The reasons for missing data values, drop-out, and protocol departures will have been documented in/with the database.
- (3) The plan also includes outcome-dependent exploratory analyses to generate new hypotheses.
- (4) Descriptive graphical and tabular methods will be used to characterize the participants, visualize the data, and examine relationships among variables.
- (5) To indicate precision, all statistical estimates of population parameters will be tabulated along with corresponding confidence intervals (CI) or standard errors (SE). The CI will be interpreted as the set of potential values of the population parameter that are most compatible with the observed data.
- (6) All hypothesis tests yielding p-values that are deemed to be not statistically significant will be reported as being inconclusive. The proposed statistical analysis strategy acknowledges that no p-value can reveal the plausibility, presence, truth, or importance of an association or effect-- which is consistent with the statements of the American Statistical Association [4,5], the recommendations in Nature [6,7], and guidance, such as the CONSORT Statement [1], STROBE Statement [2], and ICMJE guidance [3].²

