9.4. Plans for Coping with Withdrawals and Loss-To-Follow-Up

Enrolled participants who discontinue treatment/or withdrawn from study will not be replaced. Allowing for a 20% drop out rate, approximately 55 - 60 subjects will be enrolled.

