9.5. Sample Size Rationale

Tolerability: The sample size for tolerability was not determined from power analysis but based on multiple previous clinical trials conducted with GOS⁵⁸⁻⁶¹.

Microbiome: Our previous studies^{10, 11, 31, 32} conducted with a different but equivalent GOS preparation (purified prebiotics) have demonstrated a consistent and statistically significant increased abundance of the targeted beneficial bacteria: *Bifidobacterium* and *Akkermansia*. The proposed pilot study will recruit

60 subjects. After estimated dropout rate of 20%, the final subjects that will complete the subject will be N=48, which is 16 for each arm. This sample size is chosen given limited funds available with the pilot award supporting this project.

Biomarkers of inflammation: Since this is the first study, we do not have the estimate of effect size so the power cannot be computed. Additionally, due to the limitation of the funding with n=20, we do not expect to have sufficient power to detect differences over time. In that case, we will perform an exploratory analysis of changes in plasma cytokines and biomarkers of inflammation and compare the summary statistics such as mean and standard error.

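### Simple randomisation in Section 6.2 gives the stated 16 per arm only on average; a concealed permuted-block list would secure it at almost no cost

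*Combined protocol and SAP*

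**What the plan says.** Section 6.2 gives the whole method in one sentence: "The Excel RAND function will be used for simple randomization of participants into the 3 different groups". The entry under "Matching and Stratification" is N/A. The master codes are kept by IDS. No section mentions blocks, a cap on arm size or a pre-built list, and none says who generates the sequence.

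Elsewhere the arm size is stated as settled. Section 4.2 has "Subjects will be assigned randomly to one of 3 groups (n = 16): GOS, hGOS or placebo", and the Synopsis and Sections 2.3 and 4 agree. Section 9.5 attaches the same figure to completers: "After estimated dropout rate of 20%, the final subjects that will complete the subject will be N=48, which is 16 for each arm".

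The number randomised is not consistent. Section 8.6 has "A total of 45 individuals will be randomized 1:1:1 (placebo, GOS, hGOS) to treatment". The Synopsis and Section 5.1 give 48 enrolled from 55-60 screened. Section 9.4 has "Allowing for a 20% drop out rate, approximately 55 - 60 subjects will be enrolled". The same 20% serves as the screen-failure rate in Sections 5.1 and 5.3 and as the dropout rate in Sections 9.4, 9.5 and 9.6.

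**The concern.** Under simple randomisation each participant is assigned independently, so arm sizes are random. The protocol therefore promises a property that the named method lacks.

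Two uses of the data depend on arm size:

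- Aim 1, the primary aim, is reported as percentages with confidence intervals (Section 9.2), and their width is set by the number in the arm. Withdrawals are not replaced (Section 9.4), so a short arm stays short.
- Sections 6.7, 10.2 and 10.4 provide for a pause based on the first 20 enrolled. In Sections 6.7 and 10.2 the unblinded medical monitor then judges whether events sit in one arm or spread across arms. That judgement is hard to make if one arm has only three or four people at that point.

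**Working it through.** **The plan's own figure.** 60 × (1 − 0.20) = 48 = 3 × 16, so Section 9.5 reproduces, but 16 is then the expected number of completers per arm.

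**Arm sizes.** Under simple 1:1:1 allocation, P(a, b, c) = N! / (a! b! c!) × 3^(−N). For example, 48! / (16!)³ / 3⁴⁸ = 0.017. Exact enumeration over all splits gives:

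| N randomised | P(exactly equal) | Expected smallest arm | Expected largest arm | P(smallest ≤ 12) |
|---|---|---|---|---|
| 45 (Section 8.6) | 1.8% | 11.8 | 18.3 | 61% |
| 48 (Synopsis, Section 5.1) | 1.7% | 12.7 | 19.4 | 41% |
| 60 (Section 9.5) | 1.4% | 16.3 | 23.8 | 5% |

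**Completers, 60 randomised.** Assume 20% dropout, random and unrelated to arm.
- Simple: each of the 60 is a completer in a given arm with probability 0.8/3 = 0.267. By simulation, P(some arm has ≤ 12 completers) is about 43%.
- Equal allocation: each arm is binomial(20, 0.8) and P(≤ 12) = 0.032. Over three arms, 1 − (1 − 0.032)³ is about 9%.

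**Precision of a per-arm percentage.** With no events, the exact 95% upper limit is 1 − 0.025^(1/n): 20.6% at n = 16, 26.5% at n = 12 and 30.8% at n = 10.

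**Precision of a two-arm contrast.** The standard error is proportional to √(1/n₁ + 1/n₂).
- 16 v 16: √(2/16) = 0.354.
- 12 v 18: 0.373, about 5% larger.
- 10 v 19: 0.391, about 10% larger.

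Over all allocations at N = 48, the standard error is about 2% larger on average and 10% larger at the 90th percentile. The plan gives no effect size ("we do not have the estimate of effect size so the power cannot be computed"). At an assumed standardised difference of 1.0, two-sided 0.05, power is 80.7% at 16 v 16, 76.5% at 12 v 18, 72.6% at 10 v 19, and 79.1% on average under simple randomisation.

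**First 20 enrolled.** The same formula with N = 20 gives P(smallest arm ≤ 4) = 44% and P(≤ 3) = 18%. The largest arm is at least twice the smallest in 48% of draws. With blocks of 3 and 6, every arm has 6 to 8.

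**Order of enrolment, N = 48.** Compare arms on the share of their members among the first 24 enrolled. The expected difference is zero. By simulation, a given pair differs by 25 points or more in 17% of allocations, and at least one of the three pairs does in 36%. A list shuffled at fixed 16/16/16 gives 22% and 43%. Reading these as calendar halves of the 40 weeks further assumes even accrual, which the protocol does not state.

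**What mixed blocks deliver.** Arms never differ by more than two at any point. A list cut at 48 falls halfway through a block of 6 about one time in three. The three assignments made by then are not one per arm with probability 12/20. So 1/3 × 0.6 = 20% of lists end 17/16/15, and the rest end 16/16/16.

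**The case against.** The strongest case is that little is lost. The trial is a pilot sized by funding, Aim 1 is descriptive, and no power claim is broken. Simple randomisation is unbiased, and a precision loss averaging 2% would hardly be noticed. The sizes in Section 9.5 also start from 60 recruited; if 60 are randomised, an arm of 12 or fewer at randomisation occurs in 5% of draws, not 41%. Dropout disturbs 16 per arm under any scheme. All of this stands, and it is why the point is an improvement and not a flaw in validity.

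It can also be said that RAND may be meant to sort a prepared 16/16/16 list, since the codes are held in advance. That would fix the totals. But Section 6.2 does not describe such a list, and that would not be simple randomisation. It would also leave the order of enrolment, and so the first 20, unbalanced. The text needs correcting on either reading.

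A reader might go further and infer that, with enrolment estimated at 40 weeks, the comparison is confounded with season. The documents do not support that. Allocation is independent of enrolment date, so any imbalance is by chance and is already carried in the standard errors. The between-arm tests in Section 9.2 use change over four weeks, which removes stable seasonal differences in level. No section mentions season, so an effect of season on these outcomes would be an assumption. The 36% above is the worst of three pairs; for any one contrast it is 17%.

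**Conclusion.** The point holds in limited form. Sections 4.2, 8.6 and 9.5 state a balance that the method in Section 6.2 gives only in expectation, whichever total is used. Exact equality has a probability below 2% at 45, 48 or 60. The practical cost lies in the poor draws: a wider interval for tolerability in the short arm, and a weak by-arm comparison among the first 20.

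The arm-size figures are exact and need only independent 1:1:1 assignment. The completer figures also assume 20% dropout at random. The power figures rest on an assumed effect and are illustrative. Bias, invalid tests and seasonal confounding are not shown. The change should be made, but the trial would be interpretable without it.

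**What to change.** 1. Reconcile the number to be randomised across the Synopsis and Sections 5.1, 8.6, 9.4 and 9.5 (45, 48 or 55-60), and state whether 16 per arm means randomised or completing.
2. In Section 6.2, replace simple randomisation with a computer-generated 1:1:1 permuted-block list with randomly varying blocks of 3 and 6. IDS generates and holds it, and block sizes are not disclosed to the study team.
3. If the scheme is kept, describe 16 per arm as an expected size wherever it appears.

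The cost is a short text change and one list, prepared before the first participant is randomised. IDS already holds the codes. Blocking adds slight predictability, which double blinding and concealed, varying block sizes limit. Totals may end 17/16/15 in about 20% of lists at 48.
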